7.3. Lost to Follow-up

The following actions must be taken if a participant fails to return to the clinic for a required study visit:

- The site must attempt to contact the participant and reschedule the missed visit as soon as possible and counsel the participant on the importance of maintaining the assigned visit schedule and ascertain whether or not the participant wishes to and/or should continue in the study.
- Before a participant is deemed lost to follow-up, the investigator or designee must make every effort to regain contact with the participant (where possible, [3] telephone calls and, if necessary, a certified letter to the participant's last known mailing address or local equivalent methods). These contact attempts should be documented in the participant's medical record.
- Should the participant continue to be unreachable, he/she will be considered to have withdrawn from the study and lost to follow-up.
 - The rules for handling missing data for an individual participant will be specified in [Section 9](#) and the SAP for the study.

Discontinuation of specific sites or of the study as a whole are handled as part of Study and Site Start and Closure [Section 10.1.9](#).

8. STUDY ASSESSMENTS AND PROCEDURES

- Study procedures and their timing are summarized in the SoA.
- Immediate safety concerns should be discussed with the sponsor immediately upon occurrence or awareness to determine if the participant should continue or discontinue study intervention.
- Adherence to the study design requirements, including those specified in the SoA, is essential and required for study conduct.
- All screening evaluations must be completed and reviewed to confirm that potential participants meet all eligibility criteria. The investigator should maintain a screening log to record details of all participants screened and to confirm eligibility or record reasons for screening failure, as applicable.
- Procedures conducted as part of the participant's routine clinical management (eg, blood count) and obtained before signing of the ICF may be utilized for screening or baseline purposes provided the procedures met the protocol-specified criteria and were performed within the time frame defined in the SoA.
- The maximum amount of blood collected from each participant over the duration of the study, including any extra assessments that may be required, will not exceed 415 mL.
- Repeat or unscheduled samples may be taken for safety reasons or for technical issues with the samples.

8.1. General Administrative Procedures

8.1.1. Informed Consent

The investigator or medically qualified designee (consistent with local requirements) must obtain documented consent from each potential participant/legal representative prior to participation in this study. A signed copy of the ICF should be given to the participant and the original should be placed in the participant's medical records.

8.1.2. Assignment of Participant Number

Each participant who signs the ICF will be assigned a unique number that will identify the participant throughout the study. Once a number has been assigned, it cannot be reassigned to another study participant. See [Section 5.4](#) for handling of participant numbers for screen failures who are rescreened.

8.1.3. Primary Diagnosis and Prior Treatment

The primary diagnosis and prior treatment(s), including best response and time to progression, if available should be recorded.

8.1.4. Medical History

A medical history will be obtained by the investigator or a medically qualified designee (consistent with local regulations). All active conditions should be recorded and any condition diagnosed within the last 1 year that the investigator deems clinically significant.

8.1.5. Demographics

Demographics will include race, ethnicity, age, and sex.

8.1.6. Medication Review (Prior and Concomitant Medications)

The investigator or medically qualified designee should review the participant's prior medication use within 30 days of the Screening assessment. All medication currently taken by the participant should be recorded.

8.1.7. Inclusion and Exclusion Criteria Review

All inclusion and exclusion criteria should be reviewed by the investigator to ensure the participant qualifies for the study.

8.2. Efficacy Assessments

Planned time points for all efficacy assessments are provided in the SoA. The efficacy assessments will measure antitumor activity and include:

- ORR, PFS, TTR, DOR, DCR
- OS

Antitumor activity will be assessed by radiological tumor assessments and will be based on RECIST v1.1 criteria.

The details related to tumor assessments are presented in [Appendix 8](#).

8.3. Safety Assessments

Planned time points for all safety assessments are provided in the SoA. The safety assessments include:

- AEs and SAEs
- Laboratory measurements
- Other laboratory measurement (AAGP)
- Physical examination findings
- Vital signs
- ECG findings

Any clinically significant changes in laboratory findings, PE findings, vital sign measurements, and ECG findings occurring during the study must be reported as an AE.

8.3.1. Physical Examinations

- A complete PE will be conducted according to the SoA (Table 3). Weight will be collected at Day 1 of each cycle. Height will be collected at Screening only.
- Investigators should pay special attention to clinical signs related to previous serious illnesses.
 - Any abnormalities identified at the screening PE should be recorded as medical history.
 - Any abnormalities identified after the screening PE should be recorded as an AE.

8.3.2. Vital Signs

- Temperature, pulse rate, respiratory rate, and BP will be assessed per institutional guidelines.
- If not otherwise directed by institutional guidelines, BP and pulse measurements should be preceded by at least 5 minutes of rest for the participant in a quiet setting without distractions (eg, television, cell phones).

8.3.3. Electrocardiograms

- A single 12-lead ECG will be obtained as outlined in the SoA (Table 3) using an ECG machine that automatically calculates the HR and measures PR, QRS, QT, and QTc intervals.

8.3.4. Clinical Safety Laboratory Assessments

- See Appendix 3 for the list of clinical laboratory tests to be performed and to the SoA (Table 3) for the timing and frequency.
- The investigator must review the laboratory report, document this review, and record any clinically significant changes occurring during the study as an AE. The laboratory reports must be filed with the source documents.
- Abnormal laboratory findings associated with the underlying disease are not considered clinically significant unless judged by the investigator to be more severe than expected for the participant's condition.
- All laboratory tests with abnormal values considered clinically significant during participation in the study and/or considered by the investigator to be related to study drug should be repeated until the values return to normal or baseline or are no longer considered clinically significant by the investigator.
 - If clinically significant values do not return to normal/baseline within a period of time judged reasonable by the investigator, the etiology should be identified, and the sponsor notified.
 - All protocol-required laboratory tests, as defined in Appendix 3, must be conducted in accordance with the SoA (Table 3).

- Any participants with febrile neutropenia of any grade, Grade 4 neutropenia, and/or Grade 4 thrombocytopenia, should have relevant tests repeated daily until recovery to Grade ≤ 3 and through the day after fever resolution, if applicable.
- For Cycle 3 and after, Hematology and Biochemistry “A” tests on Days 8 and 15 are to be performed only in participants with Grade ≥ 3 biochemical or Grade 4 hematological treatment-related toxicities, or who required dose adjustments due to hematological or biochemical abnormalities in the preceding cycle (Table 3).

8.3.5. Other Laboratory Assessment

Levels of serum AAGP will be assessed.

8.3.6. Pregnancy Testing

- Refer to Section 5.1 Inclusion Criteria for pregnancy testing entry criteria.
- Pregnancy testing (urine or serum as required by local regulations) should be conducted according to the SoA (Table 3).
- Pregnancy testing (urine or serum as required by local regulations) should be repeated 30 days after last dose of lurbinectedin.
- Additional serum or urine pregnancy tests may be performed, as determined necessary by the investigator or required by local regulation, to establish the absence of pregnancy at any time during the participant's participation in the study.

8.4. Adverse Events, Serious Adverse Events, and Other Safety Reporting

The definitions of AEs and SAEs can be found in Appendix 4.

AEs will be reported by the participant (or, when appropriate, by a caregiver, surrogate, or the participant's legally authorized representative).

The investigator and any qualified designees are responsible for detecting, documenting, and recording events that meet the definition of an AE or SAE and remain responsible for following up all AEs (see Section 7).

The method of recording, evaluating, and assessing causality of AEs and SAEs and the procedures for completing and transmitting SAE reports are provided in Appendix 4.

8.4.1. Time Period and Frequency for Collecting AE and SAE Information

All AEs and SAEs will be collected from the start of intervention until the EOT or E/D visit as specified in the SoA (Table 3) and per Section 8.4.3. Participants' discontinuation from study treatment with an ongoing treatment-related AE should be followed until satisfactory resolution per the investigator. Any spontaneous reporting of treatment-related SAE during the OS follow-up will be also collected and reported.

Note: All SAEs that occur after the consent form is signed but before study intervention/treatment must be reported by the investigator if they cause the participant to be

excluded from the trial, or are the result of a protocol-specified intervention, including but not limited to diet, placebo treatment, or a procedure.

Medical occurrences that begin before the start of study intervention but after obtaining informed consent will be recorded as Medical History/Current Medical Conditions, not as AEs.

All SAEs will be recorded and reported to the sponsor or designee immediately and within 24 hours of first knowledge of the event by study personnel, as indicated in [Appendix 4](#). The investigator will submit any updated SAE data to the sponsor within 24 hours of it being available. All treatment-related deaths will be reported as SAEs. Deaths due to progression of disease are not SAEs and should not be reported as SAEs.

Investigators are not obligated to actively seek information on new AEs or SAEs after conclusion of the study participation. However, if the investigator learns of any SAE, including a death, at any time after a participant has been discharged from the study, and he/she considers the event to be reasonably related to the study intervention or study participation, the investigator should promptly notify the sponsor.

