1.3. Schedule of Activities

Table 3: Schedule of Activities

Procedure	Screening (window)	Intervention Period [Days]							EOT (30± 7D after last dose) or E/D	OS telephone call every 3 months	Comments
		C1		C2		≥ C3					
		D1	D8	D15	D1	D8	D15	D1			
Informed consent	X (-28 to -1)										
Inclusion and exclusion criteria	X (-28 to -1)										Note: for the HRD-positive malignancies agnostic cohort, participants without mutational analysis results are not eligible for participation
Demography	X (-28 to -1)										
Primary diagnosis and prior treatment(s)	X (-28 to -1)										
Medical and cancer history/past and current medical conditions	X (-28 to -1)										

Procedure	Screening (window)	Intervention Period [Days]							EOT (30± 7D after last dose) or E/D	OS telephone call every 3 months	Comments
		C1		C2			≥ C3				
		D1	D8	D15	D1	D8	D15	D1			
Full physical examination including height, weight, and BSA	X (-7 to -1)	X			X			X		BSA will be recalculated on Day 1 of each treatment cycle. The dose of study intervention should be recalculated if the participant's BSA has a ≥ 10% change (higher or lower) compared with the predose CID1 value or the BSA recorded for dosing calculation at the previous cycle (see Section 5.5.1). Height is only required at Screening.	
Performance status (ECOG)	X (-7 to -1)	X			X			X		-1 day window (except in Cycle 1)	
Single 12-lead ECG	X (-7 to -1)									ECG: cardiac rhythm will be identified in ECG intervals of at least 30 seconds of duration, PR interval, QT interval (raw), heart rate (HR) and QRS complex.	
Highly sensitive serum OR urine pregnancy test (WOCBP only)	X (-7 to -1)	X			X			X		Beta subunit-human chorionic gonadotropin (β-hCG) (urine or serum). In WOCBP, if a urine pregnancy test is positive a serum test must be performed and confirmed negative prior to administering IP. See Section 8.4.5 for pregnancy reporting requirements.	

Procedure	Screening (window)	Intervention Period [Days]							EOT (30± 7D after last dose) or E/D	OS telephone call every 3 months	Comments
		C1		C2			≥ C3				
		D1	D8	D15	D1	D8	D15	D1			

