HIV (antibody), Hepatitis B (surface antigen), and Hepatitis C (surface antigen, and RNA if positive by antibody) screening	X (-28 to -1)									
 D-1 is the calendar day before C1D1. Screening assessments must be repeated if the first infusion of lurbinectin is given outside the stated window. EOT is defined as 30 days after the last dose of lurbinectin, unless the participants starts any subsequent anticancer therapy, in which case the EOT visit should be performed immediately before the start of new therapy. The EOT assessments will be performed if no recent data are available (ie, within the previous 10 days prior to the EOT visit) or if the last available data show a Grade ≥ 2 increase in AE severity. 
All participants will be tested for HIV prior to the enrollment into the study and HIV-positive participants will be excluded from the study. Participants with active hepatitis B (chronic or acute; defined as having a positive HBsAg test result at screening) will be excluded from the study. Participants with past or resolved HBV infection (defined as the presence of HBcAb and absence of HBsAg) are eligible; HBV DNA should be obtained in these participants prior to enrollment. Participants with HCV will be excluded from the study; participants who test positive for HCV antibody are eligible only if PCR is negative for HCV RNA.
	
Coagulation tests	X (-7 to -1)							X		-3 day window (except in Cycle 1). Clinical laboratory tests are detailed in Appendix 3.	

Procedure	Screening (window)	Intervention Period [Days]							EOT (30± 7D after last dose) or E/D	OS telephone call every 3 months	Comments
		C1		C2			≥ C3				
		D1	D8	D15	D1	D8	D15	D1			

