7.1. Discontinuation of Study Intervention

In rare instances, it may be necessary for a participant to permanently discontinue study intervention. If study intervention is permanently discontinued, the participant will return to the site 30 days (± 7 days) later for an EOT visit, and the participant will be followed for OS. For participants who discontinue treatment due to reasons other than disease progression, death, withdrawal of consent from study, or lost to follow-up, radiographic assessment should continue until disease progression, initiation of new anticancer therapy, death, withdrawal of consent from study, EOT Visit, lost to follow-up, or study termination. A radiological tumor assessment will be performed at the EOT visit for these participants if not performed within 7 days of the last treatment assessment visit. See the SoA (Table 3) for data to be collected at the time of discontinuation of study intervention and follow-up and for any further evaluations that need to be completed.

A participant must be discontinued from study intervention for any of the following reasons:

- The participant requests to discontinue study intervention
- The participant has an AE that may compromise the participant's continued participation (see Section 8.4.3 for follow-up guidelines)
- The participant experiences a Grade ≥ 3 hypersensitivity reaction
- The participant experiences Grade ≥ 3 rhabdomyolysis
- The participant has any of the clinical conditions as noted in Section 6.7, which cannot be resolved with either of the following attempts:
 - The participant requires > 2 dose reductions
 - The participant requires a treatment delay > 3 weeks from the due date because of treatment-related toxicity (except if objective clinical benefit is observed, with the Sponsor's agreement)
- The participant has a positive serum pregnancy test or becomes pregnant during the study (Appendix 5 and Section 8.4.5)
- The participant is noncompliant with study intervention or procedures
- The sponsor decides to terminate the study or an individual cohort for any reason
- The investigator determines the participant should not continue on study intervention

- The participant has confirmed radiological disease progression as per RECIST v1.1

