7.2. Participant Discontinuation/Withdrawal From the Study

- A participant may withdraw from the study at any time at his/her own request or may be withdrawn at any time at the discretion of the investigator for safety, behavioral, or compliance reasons.
- At the time of discontinuing from the study, if possible, an E/D visit should be conducted within 30 days, as shown in the SoA. See SoA for data to be collected at the time of study discontinuation and follow-up and for any further evaluations that need to be completed.
 - The participant will be permanently discontinued from both the study intervention and from the study at that time.
- If the participant withdraws consent for disclosure of future information, the sponsor may retain and continue to use any data collected before such a withdrawal of consent.
- If a participant withdraws from the study, he/she may request destruction of any samples taken and not tested, and the investigator must document this in the site study records.

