9.4.1.1.2. Post-baseline

Post baseline evaluations will be defined as evaluations taken after the date of the first dose of study treatment.

The post-baseline period is further characterized into a treatment period, a 30-day safety follow-up period after the last dose of study treatment, and an OS Follow-up Period.

Treatment-emergent adverse events are defined as AEs with an onset date on or after the date of the first dose of study treatment. An AE is a TEAE if it occurs up to 30 days after the last dose of study intervention. TEAEs can be pre-treatment AEs that worsen in CTCAE grade after the start of study treatment.

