### 10.2.1. Treatment Emergent Adverse Events (TEAEs)

Treatment-emergent adverse events (TEAE) are defined as AEs with an onset date on or after the date of the first dose of the study treatment and within 30 days of last dose received (the 30-day safety window). TEAEs can be pre-treatment AEs that worsen in CTCAE grade after the start of study treatment. For the purpose of determining treatment-emergent, incomplete and missing AE start dates will be imputed as specified in [Section 7.4.3](#).

Treatment-related AEs are those for which investigators answer “Yes” to the question “Is this adverse event related to study treatment [lurbinectedin]?” in the CRF. Events for which investigators do not record the relationship to lurbinectedin will be considered as related to lurbinectedin for summary purposes. By-participant listings for those events for which the investigator does not record relationship to lurbinectedin will show treatment relationship as missing.

The severity of AEs will be recorded using the Common Terminology Criteria for Adverse Events (CTCAE), version 5.0. Adverse events are graded by the investigator as Grade 1 (mild), Grade 2 (moderate), Grade 3 (severe), Grade 4 (life threatening), or Grade 5 (fatal). The severity grade of events for which the severity was not recorded will be categorized as “missing” for summaries and listings and will be considered the least severe for the purposes of sorting for data presentation.

The following summaries of TEAEs (number and percentage of participants) will be provided overall (across all cohorts) using Safety analysis set:

Jazz Pharmaceuticals, Inc.

JZP712-201 Statistical Analysis Plan - Protocol Amendment

2

- Summary of any TEAEs by worst CTCAE grade (any grade, grade 3-4, grade 5) presented by SOC/PT
- Summary of TEAEs by PT (decreasing frequency)
  - Any grade
  - Grade 3-4
  - $\geq$  Grade 3
- Summary of any non-serious TEAEs by worst CTCAE grade (any grade, grade 3-4, grade 5) presented by SOC/PT
- Summary of treatment-related TEAEs by worst CTCAE grade (any grade, grade 3-4, grade 5) presented by SOC/PT
- Summary of treatment-related TEAEs by PT (decreasing frequency)

A by-participant TEAE listing will be provided with participant identifier, cohort, SOC, PT, start date, end date, severity grade, seriousness, relationship to lurbinectedin, and outcome of the AE using Safety analysis set.

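### Active AE and SAE collection can end before the 30-day treatment-emergent window closes, for participants whose EOT or E/D visit falls before day 30 after the last dose

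*Protocol*

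**What the plan says.** **End of collection.** Protocol 8.4.1: "All AEs and SAEs will be collected from the start of intervention until the EOT or E/D visit as specified in the SoA".

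**Timing of that visit.**
- The SoA column is headed "EOT (30± 7D after last dose) or E/D", so days 23 to 37 after the last dose are all compliant.
- If the participant starts another anticancer therapy, the SoA overrides this: "in which case the EOT visit should be performed immediately before the start of new therapy". It sets no earliest day.
- Section 7.1 says that after permanent discontinuation "the participant will return to the site 30 days (± 7 days) later for an EOT visit". Read literally, the count runs from discontinuation, whereas the SoA counts from the last dose.
- Section 7.2 says of a participant leaving the study that "if possible, an E/D visit should be conducted within 30 days, as shown in the SoA". That count runs from leaving the study, and no minimum time after the last dose is set.

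**Analysis window.** Protocol 9.4.1.1.2: "An AE is a TEAE if it occurs up to 30 days after the last dose of study intervention". SAP 7.3.1 repeats this. SAP 10.2.1 limits TEAEs to onset after first dose "and within 30 days of last dose received (the 30-day safety window"). SAP 10.2.2 to 10.2.4 apply the same window to SAEs, discontinuations and dose modifications. Neither document shortens the window at the visit or at new therapy.

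**Collection that continues after the visit.** Section 8.4.1 follows ongoing treatment-related AEs and accepts spontaneous reports of treatment-related SAEs during survival follow-up. Section 8.4.3 follows reported SAEs to an outcome. Section 4.1 provides survival calls every 3 months, and SAP 10.2.5 tabulates deaths within 30 days of the last dose.

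**The concern.** The tables count events over 30 days, but the protocol does not require anyone to look for new events over all of those days. The AE tables give numbers and percentages of the Safety analysis set, with no adjustment for time observed. A participant whose collection stopped on day 23 therefore counts the same as one followed to day 30, and the remaining days are treated as event-free. The error can run in only one direction, towards under-counting.

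The gap may also be selective. The rule that moves the EOT visit forward applies to participants who switch therapy soon after the last dose, and early progression is one route to that.

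The two documents also draw the boundary differently. In the protocol (4.1 and 4.4) survival follow-up begins after the EOT visit. In SAP 7.2.2 it begins after the 30-day safety period. The days between an early visit and day 30 are survival follow-up for the site and safety follow-up for the analyst. Safety is a stated secondary objective, so the tables should mean what their definition says.

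**Working it through.** The plan gives no figure of its own to reproduce. The check is day arithmetic.

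**Inputs from the documents.** TEAE window W = 30 days after last dose (protocol 9.4.1.1.2; SAP 7.3.1, 10.2.1). Routine EOT visit at 30 ± 7 days after last dose (SoA). No earliest day if new therapy starts (SoA) or for an E/D visit (7.2).

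**Gap for one participant.** Days without active collection = max(0, W − visit day).
- Earliest routine visit: 30 − 7 = day 23. Gap 30 − 23 = 7 days; 7/30 = 23.3%.
- Visit on days 30 to 37: gap 0.
- Visit brought forward (illustrative days, not in the documents): day 21 gives 30 − 21 = 9 days, 9/30 = 30.0%; day 14 gives 30 − 14 = 16 days, 16/30 = 53.3%.

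**Can a visit be brought forward before day 30?** With no dose delay, the second dose falls 21 days after the first. The first scan is due at 42 ± 7 days, that is 35 to 49 days after the first dose. A scan done before the third dose is due (35 to 42 days) falls 35 − 21 = 14 to 42 − 21 = 21 days after the last dose. New therapy started less than 30 − 21 = 9 to 30 − 14 = 16 days after that scan would put the EOT visit before day 30. This is possible, but the documents do not say how often it would happen. Day 14 needs the earliest scan and new therapy on the same day, so 53.3% is an extreme.

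**Share of participants affected (assumption only).** Let s be the share of routine visits before day 30 and q the share brought forward by new therapy. Share affected = q + (1 − q) × s.
- If routine visits are spread evenly over days 23 to 37, 7 of the 15 days fall before day 30, so s = 7/15 = 46.7%. The mean gap is 28/15 = 1.9 days over all visits and 28/7 = 4.0 days among early ones.
- q = 0, s = 0: 0%.
- q = 10%, s = 0: 10%.
- q = 50%, s = 46.7%: 0.5 + 0.5 × 0.467 = 73%.

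The range of 0% to 73% comes entirely from the assumed q and s.

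**Effect of the Section 7.1 anchor.** If stopping is decided at the next due date, day 21 after the last dose, 30 ± 7 days from that decision is day 21 + 23 = 44 to day 21 + 37 = 58. A routine visit then leaves no gap.

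**Which events fall in the gap.**

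| Event between an early visit and day 30 | Captured? |
|---|---|
| Death | Yes, survival follow-up; SAP 10.2.5 |
| Ongoing treatment-related AE | Followed (8.4.1) |
| SAE already reported | Followed (8.4.3) |
| New related SAE | Only if volunteered or learned of |
| New SAE not judged related | No active collection |
| New non-serious AE | No active collection |

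**The case against.** The strongest case against is that collection does not simply stop at the visit. The follow-up listed above continues. Appendix 4 records an increase in severity as a new AE, so worsening of a followed event need not be lost. Some participants have further contact: Section 8.3.6 repeats the pregnancy test 30 days after the last dose, and Appendix 8 continues tumour assessments, if feasible, in those who start new therapy before progression. Section 7.1, read literally, removes the gap for many routine visits. An E/D visit belongs to a participant who is leaving the study, so part of that loss is withdrawal itself. Holding the EOT visit before new therapy is a recognisable way of keeping another drug's toxicity out of the tables.

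Most of this stands, and it rules out several stronger readings:
- A reader might infer that the 30-day window goes unobserved for many participants. The documents give no distribution of EOT or E/D dates.
- The median PFS of 1.4 months in the cited neuroendocrine tumour study does not fill that gap. It comes from Grade 2 and 3 tumours and says nothing about time from last dose to next therapy. Protocol 2.2.2 also describes few later-line options.
- A reader might infer that no AE is collected after the visit, or that 30-day mortality is understated. The continued follow-up and SAP 10.2.5 contradict both. At most, a fatal AE judged unrelated might not be recorded as Grade 5.
- A biased comparison between cohorts is not a planned output. SAP 10.2 presents AE tables across all cohorts.

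The mismatch itself remains. None of the continuing contacts is a requirement to ask about new non-serious AEs or unrelated SAEs up to day 30. The Section 7.1 anchor conflicts with the SoA and does not displace the new-therapy rule. The end of the SoA's AE review rows was not legible in the text examined, but 8.4.1 gives the end point in words.

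**Conclusion.** The concern holds for participants whose EOT or E/D visit falls before day 30 after the last dose. For them, active collection under 8.4.1 ends before the window over which TEAEs and SAEs are reported. The unobserved part is at most 7 of 30 days (23%) for a visit inside the SoA's routine window, and can be longer when new therapy starts or the participant leaves the study. It is zero for visits on day 30 or later.

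The events at risk are new non-serious AEs, SAEs not judged treatment-related, and related SAEs that nobody reports spontaneously. Missed events count as absent in the Safety set percentages, so late TEAEs can only be under-counted.

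The individual gap of up to 7 days rests on the SoA anchor. The number of participants affected, and so the size of any under-count, cannot be derived from the documents. This is a modest, correctable disagreement between the collection rule and the analysis definition. It does not invalidate the safety analysis.

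**What to change.** **Preferred.**
- In protocol 8.4.1 and the SoA, collect AEs and SAEs until the EOT or E/D visit or 30 days after the last dose, whichever is later. Where the visit was earlier and consent has not been withdrawn, one telephone contact at day 30 is enough.
- In SAP 10.2.1, flag AEs that start after new anticancer therapy so that they can be shown separately.
- Reconcile the EOT anchor in Section 7.1 (discontinuation) with the SoA (last dose), and align 7.2, 8.4.1 and the TEAE definition with the result.

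With collection to at least day 30, the gap falls from up to 7 days, or more, to 0 for every participant who can be contacted.

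**Minimum alternative.** End the SAP's TEAE window at the earlier of day 30 and the end of active collection, and report it that way. This makes definition and collection agree but recovers no events.

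**Cost.** A short call for some participants and one flag in the AE dataset. Some events collected after new therapy cannot be attributed to lurbinectedin; the flag lets readers see them apart. Participants who have withdrawn consent will still have an incomplete window.
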